Safety and Immunologic Activity of Multiple Infusions of
APN401 Wake Forest Baptist Comprehensive Cancer Center
CCCWU 03716
ClinicalTrials.Gov: NCT03087591

Principal Investigator: [name]
Wake Forest School of Medicine
Internal Medicine - Hematology and Oncology

Co-Investigators: [name]
Wake Forest School of Medicine
Internal Medicine - Hematology and Oncology

[name]
Wake Forest School of Medicine
Internal Medicine - Hematology and Oncology

[name]
Wake Forest School of Medicine
Internal Medicine - Hematology and Oncology

[name]
Wake Forest School of Medicine
Internal Medicine – Hematology and Oncology

[name]
Wake Forest School of Medicine
Internal Medicine - Hematology and Oncology

Biostatistician: [name] [name]
Wake Forest School of Medicine
Biostatistical Sciences - Biostatistics

Research Nurse: [name]
Comprehensive Cancer Center of Wake Forest University

Safety and Immunologic Activity of Multiple Infusions of APN401
Wake Forest Baptist Comprehensive Cancer Center
CCCWU 03716

Study Coordinator: [name]
Comprehensive Cancer Center of Wake Forest University

[name]
Comprehensive Cancer Center of Wake Forest University

Data Manager:

Regulatory Coordinator: [name]
Comprehensive Cancer Center of Wake Forest University

Funding Sponsor: Apeiron Biologics

IND Number: 15989

Safety and Immunologic Activity of Multiple Infusions of APN401

Wake Forest Baptist Comprehensive Cancer Center

CCCFWU 03716

STUDY SYNOPSIS

IND AGENT	
 APN401 is a suspension of autologous peripheral blood mononuclear cells (PBMCs) transfected with siRNA that reduces Cbl-b.
INDICATION	
 Advanced solid tumors
PRIMARY OBJECTIVES	
 Determine toxicities Determine immunologic effects
SECONDARY OBJECTIVE	
 Document clinical response and survival
STUDY PHASE	
 Phase I
STUDY DESIGN	
 Open-label
MAIN INCLUSION CRITERIA	
 Signed written informed consent Histologically confirmed metastatic or inoperable solid tumor no longer responding to standard therapies Must be at least 4 weeks since prior systemic therapy, radiation and/or surgery ECOG performance status 0-1 Hematocrit $\geq 28\%$, WBC $>3000/\mu\text{l}$, and platelets $>100,000/\mu\text{l}$ Creatinine $\leq 1.6 \text{ mg/dl}$ ALT and AST <2.5 fold the upper limit of normal and total bilirubin $\leq 1.6 \text{ mg/dl}$
MAIN EXCLUSION CRITERIA	
 Pregnant or breastfeeding patients Untreated, progressing, or symptomatic brain metastasis HIV, hepatitis B, or hepatitis C (active) infection Active autoimmune disease Ongoing requirement for an immunosuppressive treatment Significant cardiovascular or pulmonary disease
TREATMENT PLAN	
 PBMC for infusions will be collected by leukapheresis the day prior to infusion. Patients will be administered three infusions separated by 4 weeks Blood will be drawn pre-therapy and at 3, 5, 9, and 10 weeks, and then every 8 weeks for immune assessments Imaging will be performed pre-therapy and 2 weeks after infusion 3 and then every 8 weeks for clinical response Six patients will be treated initially. If a dose limiting toxicity (DLT) is observed in $\leq 1/6$, than an additional four patients will be enrolled to allow evaluation of laboratory correlates. Enrollment will be suspended if $>1/6$ or $>3/12$ patients manifest DLT
LABORATORY CORRELATES	
 PBMC cytokine response Circulating immunocytes
POPULATION SIZE	
 Two to 12 eligible and evaluable patients
STUDY DURATION	
 Patients will be followed for toxicity until objective disease progression or 1 year, whichever occurs first.

Safety and Immunologic Activity of Multiple Infusions of APN401
Wake Forest Baptist Comprehensive Cancer Center
CCCWU 03716

Contents

1.0	Background	6
1.1	Adoptive cellular immunotherapy	6
1.2	Cbl-b	6
1.3	APN401	7
1.4	Phase 1 study of single infusion of APN401	7
1.5	Study rationale	7
2.0	Objectives	8
2.1	Primary	8
2.2	Secondary	8
3.0	Selection of Patients	8
3.1	Inclusion criteria	8
3.2	Exclusion criteria	9
4.0	Patient Registration	10
5.0	Treatment Plan	11
5.1	Dosing	11
5.2	Leukapheresis	11
5.3	Infusion	11
5.4	Supportive care guidelines	12
5.5	Nursing implications	13
5.7	Duration of follow-up	14

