5.0 Treatment Plan

5.1 Dosing

- 5.1.1 Leukapheresis to collect PBMC for infusion will be performed the day prior to infusion. Patients will be administered three infusions of APN401 at 50×10^6 cells/kg IV, separated by 4 weeks (reference Appendix I). Leukapheresis and administration of APN401 can be delayed up to 3 weeks at the physician's discretion. Subsequent treatment must occur 28 days after prior treatment.
- 5.1.2 Six patients will be treated initially. Should >1/6 subjects experience greater than grade 3 or 4 toxicity, further enrollment of study subjects and further administration of the study agent will stop pending assessment of the risk.
- 5.1.3 If DLT is observed in $\leq 1/6$, than an additional four patients (a total of 12) will be enrolled to allow evaluation of laboratory correlates. Enrollment will be suspended if >1/6 or >3/12 patients manifest DLT

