5.6 Duration of therapy

Patients will receive protocol therapy unless:

- 5.6.1 Extraordinary medical circumstances: If at any time the constraints of this protocol are detrimental to the patient's health, protocol treatment should be discontinued. This includes any clinical adverse event, laboratory abnormality or intercurrent illness which, in the opinion of the investigator, indicates that continued treatment with study therapy is not in the best interest of the subject.

Safety and Immunologic Activity of Multiple Infusions of APN401

Wake Forest Baptist Comprehensive Cancer Center

CCCWU 03716

- 5.6.2 Patient withdraws consent
- 5.6.3 Pregnancy: All WOCBP should be instructed to contact the investigator immediately if they suspect they might be pregnant (e.g., missed or late menstrual period) at any time during study participation. Pregnancy tests should be conducted as clinically indicated.
- 5.6.4 Disease progression: Patients who progress clinically before week 9 will be removed from study if other therapy (surgery, radiation, chemotherapy) is needed urgently.

When a patient is removed from study, the Off-Study Form/Early Termination must be completed within seven days.

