11.3.2 Sample size

A total of up to 12 patients will be treated to allow evaluation of laboratory correlates. The design allows for an interim analysis to occur after the first 6 patients are enrolled. If 1 or less experience a grade 3-4 toxicity then 4 more will be enrolled, if 3 or less experience a grade 3-4 toxicity the agent will not be considered too toxic. With this sample size, during the first stage of the trial, if the true toxicity rate is 10% (or less) the trial will stop with 11% probability, whereas if the true toxicity rate is 40% (or higher) then the trial will stop with 76.7% probability. Likewise, if the trial continues to 12 patients, if the true toxicity rate is 10% or less the probability of observing more than 3 toxicities is 1.2% and if the true toxicity rate is 40% or more then the probability of observing more than 3 toxicities is 62%.

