11.4 Analyses

Adverse events will be categorized by organ system and severity and summarized as frequency counts and percentages. Other categorical data, such as clinical response, will be summarized similarly. Measured data, such as immune response, will be summarized as medians and ranges. All tests of statistical significance will be 2-sided and p-values will generally not be adjusted for multiple comparisons.

11.4.1 **Toxicity:** APN401 will be considered tolerable if $\leq 1/6$ or if overall $\leq 3/12$ patients (i.e. an observed toxicity rate of at most 30%) experience grade 3-4 toxicity. With this design the likelihood of stopping early and rejecting the therapy as too toxic is $\leq 11.4\%$ if the true grade 3-4 toxicity rate is $\leq 10\%$ and $> 76.7\%$ if it is $> 40\%$. The overall likelihood of declaring APN401 too toxic is $\leq 1.2\%$ and $> 62\%$, respectively in these scenarios.

11.4.2 **Immune response:** APN401 will be considered immunologically active if PBMC IFN- γ production in response to anti-CD3/28 stimulation or to one or more tumor antigens is significantly increased or if neutrophil to lymphocyte ratio is significantly decreased post-therapy (week 9) compared to pre therapy. Immune responses will be summarized as medians and ranges. The effects of treatment on these markers individually will be analyzed using paired t-tests or the non-parametric counterpart. With 12 patients there will be statistical power equal to 80% to detect 1 standard deviation change in these markers following treatment. All tests will be 2-sided and $P < 0.05$ will be considered significant.

Safety and Immunologic Activity of Multiple Infusions of APN401
Wake Forest Baptist Comprehensive Cancer Center
CCCWU 03716

11.4.3 Clinical response and survival: Clinical response will be assessed by RECIST and summarized as frequency counts and percentages. Progression-free survival and overall survival are calculated from the initial infusion to confirmation of progression or death. Exploratory survival plots will be estimated using the Kaplan Meier approach and median PFS and OS will be estimated if enough events occur.

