11.5 Interim Analysis

As described above an interim analysis will occur after 6 patients are enrolled

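### The stage 1 toxicity gate has no single denominator, no minimum exposure and no replacement rule, so a patient who leaves before infusion 3 without toxicity can fill one of the six slots

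*Combined protocol and SAP*

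**What the plan says.** The plan describes the patients behind the toxicity decision on three bases.

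- **Eligible and evaluable.** The synopsis entry for population size reads "Two to 12 eligible and evaluable patients".
- **Treated.** The synopsis treatment plan starts with six treated patients, and section 5.1.2 does the same: "Six patients will be treated initially. Should >1/6 subjects experience greater than grade 3 or 4 toxicity" triggers a halt.
- **Enrolled.** Section 11.3.2 provides for "an interim analysis to occur after the first 6 patients are enrolled". Section 11.5 repeats that "an interim analysis will occur after 6 patients are enrolled".

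The tolerability criterion in section 11.4.1 (at most 1/6, or at most 3/12 overall) says only patients.

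For the operating characteristics, section 11.3.2 states that "if the true toxicity rate is 40% (or higher) then the trial will stop with 76.7% probability".

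Three infusions are planned, and the study calendar puts them on Days 1, 29 and 57. Early removal is foreseen in section 5.6.4: "Patients who progress clinically before week 9 will be removed from study", on the condition that surgery, radiation or chemotherapy is needed urgently. Section 8.2 defines DLT without a minimum number of infusions. Its window is 30 days after infusion for organ toxicity and 8 weeks for treatment-related death.

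**The concern.** Section 2.1 makes the safety of multiple infusions the primary objective. Section 1.4 reports no DLT in the earlier single-infusion study, so the new safety information has to come largely from infusions 2 and 3. A patient who stops after infusion 1 gives no information on those.

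The text does not say whether such a patient belongs to the six, how long a patient must be observed before counting as free of toxicity, or whether the patient is replaced. A patient given one infusion is both enrolled and treated, so on either wording the patient occupies a slot. Such a patient who had no DLT is a non-event with only part of the planned exposure. Unless all the risk falls at infusion 1, this makes the gate easier to pass, which is the unsafe direction for a toxicity rule. It also leaves the denominator to be settled after the toxicity data are known.

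**Working it through.** **Inputs from the plan.** Stage 1 has six patients and stops if more than one has toxicity. The unacceptable rate is 0.40 and the acceptable rate 0.10 (11.3.2, 11.4.1). Three infusions are planned.

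**Inputs assumed.** The documents give no early-leaving rate and no split of risk over infusions, so both are varied.

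**1. The plan's own figure.** With six patients each at risk p, P(stop) = 1 − (1−p)^6 − 6p(1−p)^5.

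- p = 0.40: 1 − 0.0467 − 0.1866 = 0.7667, as stated (76.7%).
- p = 0.10: 1 − 0.5314 − 0.3543 = 0.1143, as stated (11% in 11.3.2, 11.4% in 11.4.1).

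Both figures give every patient the full three-infusion risk.

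**2. Leavers carry one infusion's share of the risk.** With equal risk per infusion, q = 1 − 0.6^(1/3) = 0.1566. If m of the six receive only infusion 1:

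- P(0 events) = 0.6^(6−m) × 0.8434^m
- P(1 event) = (6−m)(0.4)(0.6)^(5−m) × 0.8434^m + 0.6^(6−m) × m(0.1566)(0.8434)^(m−1)
- P(stop) = 1 − P(0) − P(1)

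For m = 1, P(0) = 0.07776 × 0.8434 = 0.0656 and P(1) = 0.2592 × 0.8434 + 0.07776 × 0.1566 = 0.2308, so P(stop) = 0.7036.

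**3. Leavers contribute no toxicity.** P(stop) = 1 − 0.6^(6−m) − (6−m)(0.4)(0.6)^(5−m). For m = 1 this is 1 − 0.0778 − 0.2592 = 0.6630.

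**4. Leavers receive two infusions.** As step 2, with risk 1 − 0.6^(2/3) = 0.2886 in place of 0.1566.

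**5. All risk at infusion 1.** Leavers then carry the full 0.40, and P(stop) stays at 0.7667.

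Stage 1 stopping probability at a true 40% rate:

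| Leavers among six | Two infusions, equal risk | One infusion, equal risk | No toxicity from leavers | All risk at infusion 1 |
|---|---|---|---|---|
| 0 | 76.7% | 76.7% | 76.7% | 76.7% |
| 1 | 73.8% | 70.4% | 66.3% | 76.7% |
| 2 | 70.6% | 62.8% | 52.5% | 76.7% |
| 3 | 67.2% | 53.9% | 35.2% | 76.7% |

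**6. What an evaluable denominator does.** Suppose 30% leave after infusion 1, risk per infusion is equal, leavers without toxicity are replaced and leavers with toxicity are kept.

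- True 40%: rate among evaluable patients = (0.7 × 0.40 + 0.3 × 0.1566) / (0.7 + 0.3 × 0.1566) = 0.438, and P(stop) = 82.1%.
- True 10%: per-infusion risk = 1 − 0.9^(1/3) = 0.0345, rate = (0.7 × 0.10 + 0.3 × 0.0345) / (0.7 + 0.3 × 0.0345) = 0.113, and P(stop) = 14.1%, against 11.4% in the plan.

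**The case against.** The strongest reply has four parts.

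- **The plan never says that a patient who leaves early is counted as toxicity-free.** A reader might infer that it does, but the text is silent. A DLT after any infusion counts under section 8.2, adverse events are recorded up to 2 months after the test drug (8.1), and the early termination visit collects them. Leavers are therefore not automatic non-events. This stands. What remains is that a leaver without a DLT still fills a slot under the enrolled or treated wording.
- **The wording conflict is milder than evaluable against enrolled.** The evaluable wording is a population-size entry, the operative rule in 5.1.2 says treated, and enrolled in 11.3.2 and 11.5 can be read as fixing when the interim look occurs. This is fair, but none of these readings sets an exposure or observation requirement.
- **Early leaving may be rare.** Section 5.6.4 applies only when other therapy is urgently needed, and the first scheduled on-study imaging is on Day 71, after infusion 3. That limits how often it happens. It does not tell the analyst what to do when it does.
- **An evaluable set has its own bias.** Keeping leavers with toxicity and replacing those without pushes the observed rate up, as step 6 of the working shows. The set also drops patients who stop for adverse events below the DLT threshold. Both points stand, so toxicity in all treated patients must be reported alongside.

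**Conclusion.** The point holds as a gap in the definition of the safety gate: three descriptions of who is counted, no minimum exposure or observation, and no replacement rule. With one or two of six leaving after infusion 1, the stopping probability at a true 40% rate falls from 76.7% to 70.4% or 62.8% under equal risk per infusion. It falls to 66.3% or 52.5% if leavers contribute no toxicity. There is no loss if nobody leaves early or if all the risk is at infusion 1.

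A reader might go further and conclude that 76.7% is wrong or will not be achieved. The documents do not support that. The figure reproduces exactly, and any shortfall rests on an assumed number of leavers and an assumed spread of risk, neither of which they give. The supportable statement is that the plan does not secure the 76.7%.

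**What to change.** Use one denominator in the synopsis and in sections 5.1.2, 5.1.3, 11.3.2, 11.4.1 and 11.5: toxicity-evaluable patients. Define these as patients who received the planned three infusions and completed the stated observation window, or who had a qualifying toxicity at any time. Then:

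- Take the 1/6 decision on six such patients, and replace others within the existing maximum.
- State which section 8.2 window has to be complete before a patient counts as toxicity-free.
- Reconcile the event being counted. The synopsis and 5.1.3 count DLT, 11.3.2 and 11.4.1 count grade 3-4 toxicity, and 5.1.2 uses a third wording.
- Report adverse events and the toxicity rate in all treated patients next to the evaluable-set result.

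The cost is protocol wording plus time. Counting from Day 57, the 30-day window ends on Day 87 (57 + 30) and the 8-week window on Day 113 (57 + 56), and each replacement restarts that clock. In a study expected to last 12-15 months (11.6) this could be noticeable. The plan should also say that the evaluable set is slightly conservative: in the 30% example, stopping probability is 82.1% at a true 40% and 14.1% at a true 10%.

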1.0 Background

1.1 Adoptive cellular immunotherapy

One approach of addressing immune deficiencies preventing an antitumor response *in vivo* effectively applied to improve survival is to infuse immune cells activated *ex vivo*. Sipuleucel-T, an autologous cellular immunotherapy, has been approved for the treatment of metastatic prostate cancer [1]. Sipuleucel-T is manufactured from peripheral blood mononuclear cells (PBMCs) isolated during leukapheresis that are cultured *ex vivo* with PA2024, a fusion protein consisting of prostatic acid phosphatase and granulocyte macrophage colony stimulating factor, and then infused back into the patient. Other strategies of activating, expanding, and/or engineering immune cells *ex vivo* to mediate antitumor effects have exhibited considerable promise in a variety of malignancies [2,3]. Cellular immunotherapy has not been reproducibly effective, and several obstacles remain, including sustaining the *in vivo* survival and function of transferred cells and generating high-avidity tumor-reactive T cells. T-cell persistence can be transiently maintained by administering interleukin (IL)-2, but this is often associated with significant toxicity and may also promote expansion of regulatory T (Treg) cells that limit antitumor immunity [4]. The poor T-cell function often observed has been more difficult to address, as it, in part, reflects deficient expression of costimulatory proteins and/or increased expression of inhibitory ligands or suppressive cytokines by tumor cells [5]. Thus, strategies to improve T cell survival, function, and avidity are needed.

Cell processing is performed per FDA approved SOPs. They include several tests of sterility.

1.2 Cbl-b

Cbl-b (Casitas B-lineage lymphoma b), an E3 ubiquitin ligase, is a major negative regulator of lymphocyte function. It increases the threshold for naive T-cell activation by regulating T-cell receptor and CD28 costimulatory signaling [6]. Abrogating Cbl-b expression rescues IL-2 production and proliferation by naive CD28^{-/-} T cells. Following target recognition, interferon (IFN-) γ production is enhanced, and target avidity is increased. Importantly, neither proliferation or cytokine production is induced in unstimulated T cells, indicating that Cbl-b silencing enhances T cell activities only in the context of antigen stimulation and does not lead to an unwanted general activation of all lymphocytes. Tumors lack the costimulatory proteins that bind CD28, and CD28 expression is often lost on T cells that have differentiated to effector cells during repetitive stimulations [7]. Thus, disrupting Cbl-b expression in tumor-reactive T cells may provide a unique strategy for increasing autocrine IL-2 production for promoting proliferative responses and survival following tumor recognition in the absence of costimulation and may also reduce the threshold for T cell activation to allow low-avidity T cells to respond to tumors expressing limiting amounts of antigen. Cbl-b^{-/-} knock-out mice are resistant to outgrowth of transplantable and spontaneous tumors [8,9]. Adoptive transfer of Cbl-b^{-/-} CD8⁺ T cells into tumor-bearing wild-type mice resulted in detectable therapeutic activity [9-11]. Tumor resistance has been attributed to the increased responsiveness of the small number of naive tumor-reactive Cbl-b^{-/-} CD8⁺ T cells present in the polyclonal repertoire. Genetic deletion of Cbl-b or targeted inactivation of its E3 ligase activity also have been shown to license natural killer (NK) cells to spontaneously reject metastatic tumors in mouse models [12]. Cellular immunotherapy with Cbl-b^{-/-} cells or inactivation of Cbl-b E3 ligase activity does not result in

Safety and Immunologic Activity of Multiple Infusions of APN401

Wake Forest Baptist Comprehensive Cancer Center

CCCFWU 03716

significant inflammation or in autoimmunity. Thus, abrogating Cbl-b expression in effector immune cells may improve the efficacy of adoptive cellular immunotherapy of human malignancies without significant clinical toxicity.

1.3 APN401

APN401 is a suspension of viable autologous human PBMCs that have been transiently transfected with siRNA in order to reduce Cbl-b protein levels, for autologous cellular immunotherapy applications. A highly efficient transfection protocol using a commercial electroporation device is used to simultaneously transfect T, B, NK cells and monocytes with the siRNA with minimal cell damage. Using this protocol shut down of Cbl-b expression can be achieved for more than seven days in stimulated human T cells, resulting in strong enhancement of T-cell activation, cytokine production, and proliferation. Cbl-b-silenced PBMCs display a clear increase in proliferation and IL-2 and IFN- γ production in response to anti-CD3/28 stimulation. In addition, Cbl-b silencing also increases secretion of tumor necrosis factor (TNF) α and IL-17. Adoptive transfer of Cbl-b silenced murine CD8 T cells using a similar transient siRNA silencing procedure as for human cells significantly decreased tumor burden [13]. Moreover, T cells isolated from tumor-draining lymph nodes displayed sustained activated T cell function five days after Cbl-b silencing and transfer. Little toxicity was observed. No unwanted effects of autoimmunity in other tissues were observed. Thus, APN401 is a novel approach to enhance antitumor immune responses. Moreover, because of potential of limited toxicity and synergy with other cancer therapies that have a mechanistic component of immune activation, APN401 has high potential to be included in combination programs.

1.4 Phase 1 study of single infusion of APN401

The feasibility and safety of a single intravenous infusion of APN401 were evaluated in patients with refractory metastatic solid tumors [14]. Patients with active autoimmune disease or a requirement for immune suppressive drugs were excluded. PBMC were collected by leukapheresis. The following day PBMCs were transfected with Cbl-b siRNA by electroporation to produce APN401 and then infused intravenously over 30 minutes. Three to ten patients were treated in each of the three dosing cohorts in which they received a single intravenous infusion of 5, 10, or 50×10^5 cells/kg APN401. PBMC were successfully collected and transfected with Cbl-b siRNA in all patients enrolled. CD3 T cell, CD56 NK cell, CD19 B cell, and CD14 monocytes were transfected with similar efficiencies. Transfected PBMCs produced 4-fold more IFN- γ 2-fold more IL-2 in response to CD3/CD28 stimulation than PBMC that were processed and electroporated without siRNA. From 27.0 to 467×10^6 siRNA transfected PBMCs were infused. Infusions were well tolerated. Mild to moderate chills developed in most patients at the completion of the infusion. Dose-limiting toxicities were not observed. There was no immediate hypersensitivity and no evidence of autoimmune adverse effects. Stable disease observed in two patients with pancreatic cancer and one with colorectal cancer was associated with increases in PBMC responses to stimulation with CD3/CD8 and tumor-associated peptides.

